2 INTRODUCTION

2.1 BACKGROUND AND RATIONALE FOR STUDY

Plaque composition rather than degree of stenosis has been shown to play a pivotal role in the development of plaque rupture leading to acute atherothrombotic events and sudden cardiac death. Vulnerable plaque is a term that represents “the susceptibility of a plaque to rupture” (1). Autopsy studies in patients who have died of cardiac causes have shown that the most common underlying plaque morphology is a ruptured thin-cap fibroatheroma (TCFA), with superimposed thrombosis (2). Although atherosclerosis is a pan-vascular process arising from systemic inflammation, vulnerable plaques are not present diffusely but are limited in number and are most commonly located in the proximal and mid segments of the epicardial coronary vessels (and distal in the right coronary artery) (3-5). Although several plaque types have been identified which are suspected to be prone to thrombosis, pathological studies conducted after events have occurred have found that the majority of culprit lesions are TCFA, characterized by a large necrotic core with a thin (<65 µm) fibrous cap consisting of mostly type 1 collagen with few smooth muscle cells, infiltrated with macrophages and T lymphocytes (5,6). Cellular production of matrix metalloproteinases and other digestive enzymes, exacerbated by altered shear stress and focal cap calcification, are suspected to lead to plaque rupture, followed by tissue factor exposure and superimposed thrombus formation.

Most coronary events occur in individuals who would be classified as low or intermediate risk by the traditional risk factors contained in the Framingham risk score. Conversely, many individuals with an apparently adverse risk factor profile remain asymptomatic. Thus, for contemporary medicine to improve, the challenge is to find and treat those unrecognized individuals at highest risk without harming those who do not need treatment (limiting both under treatment and overtreatment). Given this pathophysiological background, the goal emerged to identify in vivo the structural, morphological, chemical, and physical properties of the such vulnerable plaques in patients, with the ultimate goal of preventing plaque rupture, thereby averting myocardial infarction (MI) and sudden cardiac death. While the coronary angiography is the gold standard for identification of obstructive CAD, the angiogram is very limited for detection of vulnerable plaque. It provides only limited information about the underlying composition of coronary plaques. Direct visualization of atherosclerosis rather than merely identifying obstructive disease may improve risk stratification for future events. Therefore, a number of intravascular diagnostic modalities have been extensively tested over the last decade. Among those most widely tested are radiofrequency intravascular ultrasound, angioscopy, optical coherence tomography and near infrared spectroscopy (NIRS) (14).

PROSPECT is a prospective study of long-term outcomes in patients presenting with ACS. At baseline, 3-vessel angiography and intracoronary imaging with grayscale and RF-IVUS were performed to evaluate the characteristics of non-culprit lesions suspected to progress over time and cause major adverse cardiac events (MACE), defined as the composite of cardiac death, cardiac arrest, MI, unstable angina or increasing angina requiring re-hospitalization (7). By multivariable analysis, the only patient-level clinical variables independently associated with nonculprit lesion MACE during follow-up were insulin-treated diabetes and previous PCI (1). No angiographic variable was strongly associated with subsequent events. However, significant independent predictors of nonculprit lesion related MACE (i.e., events arising from those specific untreated lesions) were plaque burden $\geq 70\%$ (hazard ratio [HR]: 5.03; $p < 0.001$), the presence of a TCFA by RF-IVUS (HR: 3.35; $p < 0.001$), and a minimal lumen area $< 4.0 \text{ mm}^2$ (HR: 3.21, $p < 0.001$). The presence of 2 or 3 of these 3 characteristics identified lesions with a 10% and 18% likelihood, respectively, of an event arising from that site within 3 years (7). Conversely, the 3-year nonculprit lesion-related MACE rate in $>1,650$ IVUS lesions with none of these 3 characteristics was only 0.3%, and no events arose from coronary segments with $< 40\%$ plaque area.

A recent summary of the effort to detect and treat vulnerable plaque noted that in 5 separate studies, a large plaque burden by IVUS has been associated with an increased risk of progression to a MACE culprit lesion, thus establishing the principle that vulnerable plaques can be detected. (Madder, Muller, Journal of Interventional Cardiology, Supplement, 2013). However the specificity of the detection has not been adequate to serve as a guide to therapy. A more accurate measure of suspected vulnerable plaques is needed.

As demonstrated by autopsy studies, cholesterol-rich atherosclerotic plaques, which are likely to be vulnerable plaques, have a specific near-infrared spectroscopic (NIRS) chemical signature. A TVC imaging system intracoronary catheter (InfraReDx, Inc., Burlington, Massachusetts) has been developed to identify this NIRS signature in coronary arteries of patients undergoing coronary angiography. This novel catheter uses rotation and an automated pullback to generate a longitudinal chemographic road map of the coronary artery that demonstrates the presence and location of lipid-rich plaque (LRP) whose presence could not be determined by coronary angiography. The NIRS capability has now been combined with a high-quality grayscale IVUS imaging system. The combined IVUS-NIRS catheter is FDA cleared and has obtained a CE mark. NIRS has been used in over 6,000 patients in over 80 hospitals world-wide for the detection of LRP. The safety experience for the IVUS-NIRS catheter is excellent with a profile similar to that of a standard IVUS catheter.

The algorithm identifies both “lipid-core plaque” (LCP) which is synonymous with “necrotic core plaque” (8-12) and “lipid pools” in which the cellular structure is intact, but an increased concentration of lipid is present. The inclusive term “lipid-rich plaque” (LRP) describes both lipid-core plaque and plaques containing lipid pools.

LRP appears to be the common thread linking plaque vulnerability and frank instability. It is also evident that LRP can be present in more than one artery since in many cases, atherosclerosis is a multifocal pan-coronary process (5,6). Hence delineation of plaque composition in both culprit and non-culprit lesions, and in multiple types of clinical presentations may be important. NIRS has been rigorously validated against autopsy specimens and is now established as a method to accurately identify LRP in patients (8,9).

NIRS has demonstrated that culprit lesions in patients with both non-ST elevation acute coronary syndrome (ACS) and in patients with stable angina frequently contain LRP (13). A recent study by Madder et al (JACC Interventions, 2013) demonstrated that large lipid-rich plaques, often circumferential and similar to those that will be tracked prospectively in the present study, were found at the culprit site in most patients experiencing an ST segment elevation myocardial infarction (STEMI) (14). The findings of Madder et al in 20 STEMI patients have now been reproduced in a larger group of 76 patients with STEMI studied in Sweden and in the US. (Erlinge et al, European Atherosclerosis Society Presentation, 2013). This cross-sectional study included a prospective test of the ability of a max 4mm LCBI > 400 to discriminate STEMI culprit lesions from other portions of the culprit artery. This measure was able to provide excellent discrimination, and will be utilized as a measure of a “suspected vulnerable plaque” in the prospective LRP Study.

In addition to this cross-sectional data, the NIRS signature of LRP has been linked to long-term coronary outcomes. A longitudinal study in 203 patients conducted by Omerawsingh et al demonstrated that the detection of LRP above the median in a non-culprit artery identified patients with a 4-fold increased risk of MACE over the subsequent year, thus detecting vulnerable patients (Omerawsingh et al, JACC, in press, 2013). In addition, linkages with angioscopic findings have been established. Ueda and colleagues at the Osaka Police Hospital compared angioscopic findings, which require the removal of blood to obtain a clear field of view, with NIRS findings which can be obtained more easily without the need for blood removal. Sites that were yellow by angiography also showed LRP as detected by NIRS. This equivalence is of particular importance because the finding of a yellow plaque by angiography has been proven to represent the finding of a vulnerable patient (Ohtani et al, Uchida et al Am H J, 1995). These linkages with outcome studies, which build on the equivalence of angiography and NIRS, and represent only a small number of patients, require validation. This is the purpose of the larger, definitive LRP Outcomes Study.

2.1.1 STUDY AIMS

The aim of this global, multicenter, observational study is to evaluate the correlation between the presence of non-intervened, non-flow-limiting lipid-rich plaques detected by IVUS-NIRS imaging in two or more coronary arteries and the future development of a Major Adverse Cardiac Event (MACE) within the subsequent 24 months post imaging.

Endpoint: The primary outcome variable is Non-Culprit Major Adverse Cardiac Events (NC-MACE) defined as the composite of:

- cardiac death,
- cardiac arrest,
- non-fatal myocardial infarction (MI),
- acute coronary syndrome,
- revascularization by CABG or PCI,
- rehospitalization for progressive angina, adjudicated to a non index -culprit lesion secondary to significant fixed, non-reversible (not-spasm related) lesion progression of more than 20% from the baseline study (confirmed by either serial angiography or by necropsy).

Follow-up: All patients with a large LRP (defined as at least one 4 mm length of artery with a LCBI \geq 250 as assessed by IVUS-NIRS imaging) will be followed for 24 months to determine the occurrence of MACE. Patients without a large LRP will be randomly allocated in a one to one ratio to a 24 month follow-up, or no follow-up.

Blinding: The results of NIRS imaging will be partially blinded to minimize the possibility that detection of excess lipid will lead to bias created by activities such as overtreatment of LRP and/or over-reporting clinical symptoms. Treatment of the Index Culprit Artery (or arteries) will be performed in an unblinded manner with full access by the clinical site to the results of IVUS-NIRS imaging. For NIRS imaging performed for research purposes in a non-culprit artery, the clinical site will be blinded to the NIRS results. The clinical site will not be blinded to the IVUS results in the non-culprit artery.

2.1.2 PRIMARY HYPOTHESES

Two hypotheses will be tested for plaques at non-stenotic sites that have not undergone PCI:

First, patients with increased max 4mm LCBI in all scanned arteries are more likely to experience NC-MACE than those without increased max 4mm LCBI (the vulnerable patient hypothesis);

Second, coronary artery segments (defined as the proximal, mid, and distal segments of the major epicardial arteries,) with increased max 4mm LCBI (within the segment) are more likely than segments without increased max 4mm LCBI to cause NC-MACE (the vulnerable plaque hypothesis).

The portion of the coronary artery or arteries to be studied will meet all of the following criteria:

- The portion of the coronary artery does not contain a flow-limiting stenosis, defined as > 50% diameter stenosis by visual angiographic estimate;
- The portion of the coronary artery has not undergone PCI in the past, and PCI is not performed at the index event or planned in a staged procedure. The length of artery excluded from the study because of PCI includes a 5mm border on either side of the intervened segment.

3 ENDPOINTS

3.1 PRIMARY BASELINE MEASUREMENTS AND ENDPOINTS

For the Test of the Vulnerable Patient Hypothesis

The primary baseline measurement will be the maximum LCBI in 4 mm (max 4mm LCBI) over all scanned portions of the coronary arteries. The portion of artery to be scanned will exclude sites in which PCI has been performed in the past or will be performed in the index procedure (also excluding 5 mm borders of any site that underwent PCI).

The primary endpoint for the test of the vulnerable patient hypothesis will be the incidence of NC-MACE within 24 months.

The primary hypothesis is that risk of NC-MACE will be positively associated with max 4 mm LCBI measured as a continuous variable. The exposure-response relationship will also be evaluated for max 4 mm LCBI expressed as a binary variable above and below varying thresholds. It is hypothesized that increasing levels of max 4mm LCBI will identify increasing levels of risk for the patient of experiencing NC-MACE within 24 months following the artery imaging.

For the Test of the Vulnerable Plaque Hypothesis

The primary baseline measurement will be the maximum 4 mm LCBI detected in each proximal, mid, or distal segment of coronary artery scanned. The portion of artery to be scanned will exclude sites in which PCI has been performed in the past or will be performed in the index procedure (including 5 mm borders of any site that underwent PCI).

The primary endpoint for the test of the vulnerable plaque hypothesis will be the incidence of NC-MACE within 24 months.

The exposure-response function will be calculated for varying levels of max 4mm LCBI for each coronary artery segment. It is hypothesized that increased levels of max 4 mm LCBI in a coronary artery segment will identify increased levels of risk for that segment of causing NC-MACE within 24 months following the artery imaging.

FOLLOW-UP

All patients with a large LRP (defined as at least one 4mm segment with a max LCBI \geq 250 as assessed by IVUS-NIRS imaging) will be followed for 24 months to determine the occurrence of NC-MACE. Patients without at least one large LRP will be randomly allocated in a 1:1 ratio to 24 month follow-up or no follow-up.

3.2 SECONDARY AND TERTIARY ENDPOINTS AND SUBGROUP HYPOTHESES

The LRP Outcomes Study will produce a large amount of novel information that creates the opportunity for analysis of multiple secondary endpoints, multiple tertiary endpoints and multiple subgroups. Various methods of analysis and definitions of exposure, response and outcomes in subgroups of interest will be examined. Examples of each category and their relation to the primary endpoint are given below.

- 1) **Measures of exposure** – As stated above, the primary measure of exposure will be the Max 4mm LCBI. Additional analyses will be performed with the average LCBI, the IVUS plaque volume and other new measures of exposure that may emerge during the study.
- 2) **Outcomes** – The primary outcome will be NC-MACE (at the patient level in the Vulnerable Patient analysis and the segment level in the Vulnerable Plaque analysis) within 24 months following artery imaging.
- 3) **Methods of analysis** – As stated above, the primary method of analysis will involve estimation and testing for a positive association between max 4 mm LCBI and incidence of NC-MACE. Additional analyses of diagnostic performance will be performed for specific thresholds for max 4 mm LCBI, using the AUC and the net reclassification index as measures of performance.
- 4) **Subgroup analyses** – The relationship between exposure and response will be explored in patients with and without specific characteristics such as initial imaging presentation with ACS, diabetes, renal insufficiency, hypertension, age>65, male gender, and elevated cholesterol at baseline.
- 5) **Outcome at the Stented Site** While not a primary feature of the LRP Outcomes Study, an analysis will be performed of the impact of lipid status on the outcomes at the sited stented at the baseline study.

The LRP Study will test three secondary hypotheses about measures of patient-level risk derived from the NIRS chemogram, stated here in terms of the alternative hypothesis:

- 1) A threshold of max 4mm LCBI > 400 will identify patients at increased risk of a NC-MACE event.
- 2) An average LCBI in all scanned segments above the median will identify patients at increased risk of a NC-MACE event.
- 3) The exposure-response function described for the primary vulnerable patient analysis, viz, the relationship of max 4mm LCBI to NC-MACE, will demonstrate that higher values of max 4mm LCBI are associated with increased risk of the individual hard endpoints (non-culprit cardiac death, cardiac arrest, and non-fatal MI) included in the full NC-MACE endpoint.

The three pre-specified secondary hypotheses for the vulnerable-plaque level analysis are:

- 1) An average threshold of max 4mm LCBI > 400 in a coronary artery segment will identify patients at increased risk of a NC-MACE event caused by a culprit lesion located within that segment.
- 2) An average LCBI in a coronary artery segment above the median will identify sites at increased risk of a NC-MACE event due to a culprit lesion located in that segment.

- 3) Plaque burden >70% by grayscale IVUS plus a max 4mm LCBI>400 in a coronary artery segment will be a stronger predictor of risk that Max 4 mm LCBI>400 alone.

The following section provides written descriptions of additional tertiary hypotheses and exploratory analyses to be performed as part of the LRP Study:

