6.2 SAMPLE SIZE CONSIDERATIONS

A total of 9,000 patients will be enrolled with multi-vessel scans. It is expected based on the PROSPECT Study that at least 720 patients (8%) will experience a NC-MACE event. We expect to find approximately 3,000 patients with large LRP (max 4mm LCBI \geq 250). All 3,000 of these patients will be followed with phone calls for 2 years to identify those who have an event. We expect to observe at least 300 events in this group. From the 6,000 with no or small LRP, a random sample of 3,000 patients will also be followed to determine their event rate, and to examine with IVUS and angiograms those in whom events occur. Of the approximately 2,700 patients with large LRP who do not have an event, a 300 person sample will be selected for IVUS and angiographic analysis to investigate characteristics of the yellow spots that did not lead to events.

Vulnerable Patient Analysis

For hypothesis 1, we will test the hypothesis that there will be no association between the baseline value of max 4mm LCBI (over the entire area scanned) and the incidence of NC-MACE.

In PROSPECT registry results, the 24-month cumulative incidence of NC-MACE in patients was approximately 10%. Subsequent STEMI literature indicates that patients with large LRP will have a higher rate than that observed in PROSPECT.

For the power calculations below, we assumed 6,000 evaluable patients, an event rate between 4 and 8% in the overall LRP study, and a two-sided alpha of 0.05 with a standard deviation of 100 for max 4mm LCBI. Table 2

provides values for the power of the study to detect the following effect sizes: hazard ratio of 1.18, 1.20, and 1.22 per 100 unit increase in max 4mm LCBI (calculated in PASS 12). These results demonstrate that the study will have 80% power to detect a minimal effect size of 1.18 per 100 unit increase in the max 4mm LCBI with 6,000 patients and an overall cumulative incidence of 5% at 24 months. As described in section 5.3, interim analyses will be performed at 6 month intervals.

Table 2: Hypothesis 1: Power Calculation for Vulnerable Patient Hypothesis

2 Year cumulative incidence overall, patient level	Relative Risk per 100 unit increase in max 4mm LCBI		
	1.18	1.20	1.22
8%	0.95	0.98	0.99
7%	0.92	0.96	0.98
6%	0.88	0.93	0.97
5%	0.82	0.88	0.93
4%	0.73	0.81	0.87

Vulnerable Plaque Analysis

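### The secondary hypotheses on average LCBI, at patient and segment level, use an undefined median split where a continuous term would keep more information

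*Combined protocol and SAP*

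**What the plan says.** Section 3.2 lists three secondary hypotheses at each level. The second at patient level reads "An average LCBI in all scanned segments above the median will identify patients at increased risk of a NC-MACE event". Its segment-level counterpart reads "An average LCBI in a coronary artery segment above the median will identify sites at increased risk of a NC-MACE event". Neither gives a numerical cut. Neither says whose median is meant: all enrolled patients, the followed patients, or an external cohort.

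The primary exposure is handled differently. Section 3.1 states that "risk of NC-MACE will be positively associated with max 4 mm LCBI measured as a continuous variable", and Section 6.1 tests this with a Wald test in a proportional hazards model. Section 6.2 expresses the effect as a hazard ratio per 100 units, which is a log-linear form.

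Other uses of average or overall LCBI are lower in the hierarchy. Section 3.2, item 1, announces further analyses with average LCBI. Section 3.3 relates the LCBI of the scanned artery to the timing of MACE. Section 3.4 relates the LCBI of a 30 mm segment to events at that site. None of these names a scale or a cut.

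Section 2.1 describes a 203-patient study in which LRP above the median in a non-culprit artery went with a 4-fold risk of MACE over the next year.

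Sections 4.2 and 6.2 expect about 3,000 of 9,000 enrolled patients to have a large LRP. All of these are followed, together with 3,000 of the other 6,000.

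**The concern.** Splitting a continuous predictor at its median treats all patients on one side as alike. If risk changes steadily with the measure, the information within each half is thrown away, and a real association is missed more often than it need be. The median-split result would stand as the study's pre-specified secondary answer on average LCBI. A later continuous analysis could be set aside as exploratory.

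The second problem is definition. The followed cohort is deliberately enriched for large LRP. If average LCBI is correlated with max 4mm LCBI, the median of the followed patients is higher than the median of the enrolled patients. The phrase in the hypothesis could then describe two different groups, and a reader could not tell which group the hazard ratio refers to.

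**Working it through.** **Inputs (Section 6.2).** The plan takes 6,000 patients as evaluable, with 4% to 8% of them having an event. Its test level and spread are "a two-sided alpha of 0.05 with a standard deviation of 100 for max 4mm LCBI". The smallest hazard ratio is 1.18 per 100 units, which is per SD when the SD is 100. All of these are given for max 4mm LCBI. The documents give no SD, distribution, effect size or power for average LCBI.

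**1. Reproduce the plan's figure.** For a continuous covariate in a Cox model, power = Φ(√D × ln(HR per SD) − 1.96), where D is the number of events.
- D = 6,000 × 5% = 300, and ln 1.18 = 0.1655.
- √300 × 0.1655 = 2.867, and 2.867 − 1.96 = 0.907.
- Power = 0.818. Table 2 gives 0.82, and the text says "80% power to detect a minimal effect size of 1.18 per 100 unit increase in the max 4mm LCBI with 6,000 patients".

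The same formula reproduces all 15 cells of Table 2 within one point.

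**2. Effect of the split.** Under a log-linear effect, replacing the covariate by its above-median indicator multiplies D by ρ², the squared correlation between the two. The shapes are assumptions.

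| Assumed shape | ρ² | Events discarded | Effective events (of 300) | Power at HR 1.18 | Loss (points) |
|---|---|---|---|---|---|
| Continuous term | 1 | none | 300 | 0.818 | – |
| Uniform | 0.750 | 25% | 225 | 0.699 | 11.8 |
| Normal | 2/π = 0.637 | 36% | 191 | 0.628 | 18.9 |
| Exponential | (ln 2)² = 0.480 | 52% | 144 | 0.511 | 30.7 |

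A simulation of this cell with a Cox score test (3,000 runs per shape) gave, continuous to split, 0.81 to 0.69 for uniform, 0.82 to 0.61 for normal and 0.89 to 0.56 for exponential. The losses are 12, 21 and 33 points, close to the formula.

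**3. Range over Table 2.** Over the 15 cells (4% to 8% incidence, HR 1.18 to 1.22) the loss is 2.7 to 12.4 points for uniform, 5.6 to 19.3 for normal and 13.6 to 30.7 for exponential. The smallest loss is at 480 events and HR 1.22 with a uniform exposure, from 0.992 to 0.965. Heavier skew costs more: a lognormal exposure with sigma 0.8 loses 40 points in the 300-event, HR 1.18 cell.

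**4. Strong effects.** For two equal groups, power = Φ(√(D/4) × ln HR − 1.96). With D = 300, √75 = 8.66.
- HR 1.5: 8.66 × 0.405 − 1.96 = 1.55, power 0.94.
- HR 2: 8.66 × 0.693 − 1.96 = 4.04, power above 0.99.
- HR 4: power above 0.99.

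For comparison, with a normal exposure HR 1.18 per SD corresponds to exp(2 × 0.798 × 0.1655) ≈ 1.30 above versus below the median. An HR of 1.5 across the median corresponds to exp(0.405/1.596) ≈ 1.29 per SD, which is beyond the largest effect in Table 2.

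**5. Segment level.** 24,000 × 1.25% = 300 events, so the step 2 figures apply under the same borrowed assumptions. Like Table 3, they make no allowance for clustering.

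**6. Whose median.** Large LRP is 3,000/9,000 = 1/3 of enrolled patients and 3,000/6,000 = 1/2 of followed patients. If average and max 4mm LCBI were perfectly correlated, the followed median would be the value that separates large LRP from the rest, which is the 67th percentile of enrolled patients. With no correlation it stays at the 50th. In a bivariate normal illustration it falls at about the 56th, 58th and 62nd percentile for correlations of 0.5, 0.7 and 0.9. These correlations are assumptions.

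**The case against.** The strongest defence is that the median split is a deliberate question. Section 2.1 reports an above-median finding, says that such results need validation, and gives that as the purpose of this study. The hypothesis speaks of identifying patients, which is the language of classification. If the true effect is near the cited 4-fold risk, the split has ample power. This stands as far as it goes. But the earlier cut value is not carried over, so the plan does not define a replication of that rule. The cited study is also small by the protocol's own account.

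A second defence is that a linear term is not always better. If risk steps up near the median, the continuous test is the one that loses efficiency. That is true. However, the plan already accepts a log-linear form for max 4mm LCBI, and it gives no reason to expect a step at the median of average LCBI.

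Some stronger readings are tempting but not supported:
- **A fixed cost of 12 to 31 points.** That range belongs to one cell with borrowed assumptions and three assumed shapes.
- **Average LCBI made to look worse than max 4mm LCBI.** No comparison of the two measures is planned, and secondary hypothesis 1 at each level also dichotomises max 4mm LCBI, at 400.
- **A cut known to come from the enriched followed cohort.** The documents do not say so. The supportable point is that the reference population is undefined.
- **Continuous information lost to the study.** The lower-tier analyses name no cut and could use the full scale. They do not replace the secondary test.

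**Conclusion.** The point holds for the two secondary hypotheses on average LCBI. Each reduces a continuous measure to an above/below-median comparison whose cut and reference population are not stated. Under a log-linear effect, the split discards 25% (uniform), 36% (normal) or 52% (exponential) of the effective events. The power cost is conditional because the plan gives no assumptions for average LCBI. With those of max 4mm LCBI it is about 3 to 31 points over Table 2 for these three shapes. It would be larger with heavier skew and negligible for a very strong effect. The ambiguity of the median is material if average and max 4mm LCBI are correlated, because large LRP makes up half of followed patients but a third of enrolled ones.

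A reader might infer that the main conclusions are at risk. They are not: H1 and H2 use max 4mm LCBI on its continuous scale, and the interim rule in Section 6.3 rests on those two hypotheses alone. This is a worthwhile, low-cost improvement to secondary analyses and not an error in the primary plan.

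**What to change.** Restate secondary hypothesis 2 at each level as a positive association between NC-MACE risk and average LCBI on its continuous scale. At patient level, use a Wald test in the same proportional hazards model as H1. At segment level, use the H2 model with robust variance for clustering within patients. Report the hazard ratio per SD or per fixed unit.

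Keep the above/below-median comparison as a descriptive display, so the earlier above-median finding can still be examined. State its reference: the median of all enrolled patients (or of their segments), or a named external value.

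The cost is a change of wording in two hypotheses. No further patients or data are needed, since baseline imaging is submitted for every enrolled patient. The one drawback is the log-linear assumption, which loses efficiency if risk in fact steps near the median.
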